4. STUDY DESIGN

This is a single-center, randomized, sham-controlled, double-blind clinical study to investigate the feasibility of delivering RS-tDCS sessions for high-risk patients for suicide in the days following discharge from the CPEP or inpatient unit which they were admitted with SI or attempt. We plan to assess up to 80 adult patients for eligibility over 12 months of which 20 will be enrolled and randomized. Clinical assessments will be performed at baseline, post-treatment day 14 (14 days after the first RS-tDCS session), and follow-up day 30 and 60 (30 and 60 days after the first RS-tDCS session, respectively).

All study outcome measures are described in Table 1.

Time points		in-person	remote	
	Measures		S1 to S10	C14, C30, and C60
Eligibility screening		Х		
Informed consent		Х		
Enrollment		Х		
		Baseline		
Demographic data		Х		
General medical history		X		
Orientation tDCS session		X		
Loan agreement		Х		
	Feasibility		X*	
	C-SSRS	X		Х
	RRS	X		Х
	CAST	Х		Х
	MADRS	Х		Х
	C-SSRS SV		X	
	Side effects questionnaire		X	
	Treatment emergent event review		Х	Х
	Acceptability questionnaire		X**	
	Blinding assessment		X**	

Table 1. Study's time points and measures.

C14, C30, and C60: clinical assessments at post-treatment day 14, follow-up day 30 and follow-up day 60; CAST: The Concise Associated Symptoms Tracking; C-SSRS: The Columbia-Suicide Severity Rating Scale; C-SSRS SV: The Columbia-Suicide Severity Rating Scale – screening version; MADRS: Montgomery-Asberg Depression Rating Scale; RRS: Ruminative Responses Scale; S1 to S10: remotely supervised transcranial direct current stimulation (RS-tDCS) sessions one to ten.

*Number of completed RS-tDCS sessions per participant within three weeks of the study.

**applied only once, after the final RS-tDCS session (the tenth session).

Primary outcome measures:

Page 5 of 22 Version Date: 10/09/2023 1. Feasibility of the intervention – number of completed remotely supervised transcranial direct current stimulation (RS-tDCS) sessions, for both active and sham groups:

We expect at least 70% of the subjects to complete at least 5 of recommended 10 RS-tDCS sessions within three weeks of receiving the home-based tDCS device.

This criterion is based on a study that reported dropout rates between 22% and 25% of homebased tDCS for patients with bipolar depression (40) and that therapeutic effects with tDCS could be achieved within one week of treatment (24).

Secondary outcome measures:

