7. The level of side effects will be assessed at the end of each session on a 0 (not at all) to 10 (highest degree) scale used by Ahn et al. (2019) (37), which includes the following symptoms: 1. Itching; 2. Burning; 3. Headache; 4. Fatigue; 5. Nervousness; 6. Dizziness; 7. Difficulty concentrating. The total score is the sum of the 7 items, varying from 0 to 70. Higher scores indicate higher levels of side effects.

8. Treatment emergent event review: after each RS-tDCS session and clinical assessment, subjects will be asked "Have you had any new symptoms, new medical conditions or been started on new medication/treatment since we last saw you?". This information will help research staff to judge about potential adverse events related to the trial. In addition, changes in treatment will help researchers to account for them in data analysis and the study's results interpretation.

4.1. **STUDY INTERVENTION**

The study intervention is tDCS treatments delivered by the Soterix Medical mini-CT device (https://soterixmedical.com/research/remote/mini-CT). The device is a nonsignificant risk (NSR) device study because it does not meet the definition of a significant risk device under §812.3 (m) of the investigational device exemptions (IDE) regulation (21 CFR §812)

(https://www.accessdata.fda.gov/scripts/cdrh/cfdocs/cfcfr/CFRSearch.cfm?fr=812.3).

The Soterix Medical mini-CT device for the RS-tDCS includes: (1) 1 x 1 mini-CT tDCS device; (2) SNAPstrap headgear, a "cap"-like placement for simple positioning and uniform electrode placement; (3) SNAPpads (individually-packaged pre-moistened sponge), and snap connectors (Figure 1) (39).

[figure not shown]

Figure 1. Remotely supervised (RS-tDCS) Equipment. (1) 1 x 1 mini-CT tDCS device; (2) SNAPstrap headgear: "cap"-like placement for simple positioning and uniform electrode placement; (2a) markers for guidance in placement; (2b) electrode polarity labeling with fixed wiring. (3) SNAPpad: (3a) individually-packaged pre-moistened sponge; perforated packaging for easy opening; (3b) snap connectors. (adapted from Pilloni, G., A. et al., Brain Stimul 15(3): 707-716, http://creativecommons.org/licenses/by-nc-nd/4.0/, DOI: 10.1016/j.brs.2022.04.014). The figure at the bottom simulates an RS-tDCS session.

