Research staff with training in using home-based tDCS by the Soterix Medical will meet with the subject via HIPAA-compliant videoconference previously scheduled. Subjects will be encouraged to find a distraction-free setting to complete treatment sessions. After guiding the subject with the proper adjustment of the SNAPstrap headgear and turning on the 1 x 1 Mini-CT device, research staff will provide the device unlock codes for one-time use to the subject. All ten device unlock codes for one-time use (one for each tDCS session) are obtained previously, just after the device is programmed to active or sham. The device unlock codes for one-time use allow the device to function only once a day, just after the inclusion of the code, with the level of electric current and duration of the session determined by the protocol, both (electric current level and duration of the session) pre-programmed on the device before it is delivered to the subject. Thus, the subject cannot alter the electric current level, the duration of the session, or use the device more than once a day. After each RS-tDCS session, research staff will apply the side effects questionnaire, review the subject's current treatment ("treatment review"), ask about any new or updated mental or physical symptoms since the last assessment (adverse events review), and apply the C-SSRS - screening version (C-SSRS SV) as part of the risk assessment (please, see more details on item "9. RISK TO SUBJECTS"). After the last RS-tDCS session (the tenth session), research staff will apply the feasibility questionnaire and blinding assessment. (Table 1). To assess blinding, the subjects will be asked the following question, "What treatment do you believe you have received??"(47). There will be three possible answers: 1) "active-tDCS"; 2)

"sham-tDCS" or 3) "Don't know". If the answer is "Don't know", research staff will ask "Would you be willing to provide your best guess about the treatment you received?", and could choose from two possible replies: 1) active-tDCS; 2) sham-tDCS (47, 48). We will use the Bang Blinding Index, which varies from -1 to +1, being 1 complete lack of blinding, +1 the opposite guessing, and 0 being related to perfect blinding (48). After the tenth session, the subject will be asked to send back the equipment in the pre-paid mail package to send it back.

Clinical assessments:

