Clinical assessments with be performed at day 14 [+ 7 days], day 30 [+ 7 days], and day 60 [+ 10 days] from the first RS-tDCS session with the questionnaires described in Table 1. Thus, the duration of and individual's participation in the study will be up to 70 days.

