16. DATA AND SAFETY MONITORING PLAN

Risk to study subjects is minimized by only employing well-trained and clinically experienced personnel. Routine hospital protocols are already in place for handling in-person and over-the-phone crises.

Adverse Events (AEs) and Serious Adverse Events (SAEs)

An adverse event is "any untoward or unfavorable medical occurrence in a human subject...temporally associated with the subject's participation in the research, whether or not considered related to the subject's participation in the research." A serious adverse event (SAE) is an event where a relationship to the research study cannot be ruled out, and the event is life-threatening/results in death OR disabling/incapacitating OR requires or prolongs hospitalization OR involves an overdose OR was otherwise unanticipated, related to the study procedures. Due to the nature of this study, suicide attempts and psychiatric hospitalizations are possible to

happen during its course. These events are considered SAEs and reported as such. In most circumstances, suicide attempts and psychiatric hospitalizations are expected for this population and, as a result, non-study related. As such, these SAEs will be reported at continuing review but only unexpected reported immediately to the IRB. Suicide deaths are reported to the IRB within 48 hours of learning of the death. In addition, the report includes investigators' judgment as to whether a relationship to the research study can/cannot be ruled out.

For all AEs, the date and time of onset and outcome, course, intensity, action is taken, and causality to study treatment will be assessed. Based on the review of the circumstances and as-needed consultation with co-investigators, the PI can reclassify an AE as an SAE. If considered related to the study, unanticipated adverse events involving risks to subjects or others will be reported by the PI to IRB. For each adverse event, the treatment groups are compared in a pair-wise fashion regarding the occurrence of at least one event using Fisher's exact tests; the numbers of individual events will also be described. All subjects are included in these analyses.

Confidentiality

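### The scripted adverse-event question asks only about new symptoms, conditions or treatment, and it is the only event wording given for days 14, 30 and 60, so worsening of existing symptoms may go unelicited.

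*Combined protocol and SAP*

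**What the plan says.** Three places in the combined protocol and SAP bear on how adverse events are found.

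- **Section 4, secondary outcome 8.** The timing is "after each RS-tDCS session and clinical assessment, subjects will be asked", and the scripted question is "Have you had any new symptoms, new medical conditions or been started on new medication/treatment since we last saw you". Its stated use is: "This information will help research staff to judge about potential adverse events related to the trial".
- **Section 8, RS-tDCS sessions.** The review after each session is described differently. Staff are to "ask about any new or updated mental or physical symptoms since the last assessment (adverse events review"). The sentence opens "After each RS-tDCS session, research staff will apply the side effects questionnaire", so this wording belongs to the sessions. For the clinical assessments, Section 8 says only that they take place at days 14, 30 and 60 "from the first RS-tDCS session with the questionnaires described in Table 1". Table 1 lists a row called "Treatment emergent event review", marked for sessions 1 to 10 and for the three clinical assessments, with no wording of its own.
- **Section 16.** An adverse event is "any untoward or unfavorable medical occurrence in a human subject" that is associated in time with taking part. For each adverse event, the arms are compared by Fisher's exact test on whether a subject had at least one such event.

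**The concern.** Every subject enters with a mood or bipolar disorder and a recent admission with suicidal ideation or behavior, and Section 2 itself mentions residual symptoms in the first weeks after discharge. In such a group, aggravation of low mood, anxiety or poor sleep that was already there is a plausible unfavorable event. A subject with exactly that experience can truthfully answer no to the Section 4 script. The Section 16 definition would include the event, but an event that nobody asks about is unlikely to reach the adverse-event record or the Fisher comparison. The sessions carry a second, wider wording and the clinical assessments do not, so the same change may be elicited at one visit and missed at another.

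**Working it through.** The plan states no figure on this point. The check sets the texts side by side, and then asks whether a size can be given.

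**Step 1. What is asked, and when**

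| Contact | Section 4 script (new only) | Section 8 wording (new or updated) | Other prompts at the same contact |
|---|---|---|---|
| Sessions 1 to 10 | Yes | Yes | Seven-item side-effects rating; C-SSRS screening version; staff concern item (Section 9) |
| Days 14, 30 and 60 | Yes | Not given | C-SSRS, RRS, CAST and MADRS; staff concern item (Section 9) |

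Two different enquiries apply at the sessions, and only the narrower one is written for the clinical assessments.

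**Step 2. Trace one case.** A subject has insomnia at baseline. By day 30 it is worse, with no new symptom and no new treatment.

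- Section 4 script: a truthful no.
- Section 8 wording: would probably prompt a yes at a session, if updated is read to include worsened; it is not written for day 30.
- Section 16 definition: not limited to new onset, so the worsening is within scope.
- MADRS and CAST: the score may rise, but nothing in the documents turns a score change into an adverse-event record.

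**Step 3. Vary the case.** If the worsening brings a new symptom or a newly started drug, the script catches it. If it leads to a suicide attempt or a psychiatric admission, Section 16 treats it as a serious adverse event whatever the script says. The exposed group is worsening without any of these.

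**Step 4. Can the number missed be computed?** Write p_new for the share of subjects with any new symptom, p_worse for the share with worsening of an existing one (taken as independent), and c for the share of otherwise missed subjects who are picked up by another route. Then:

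missed = 20 × (1 − p_new) × p_worse × (1 − c)

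Only the 20 comes from the plan (Section 17). Assume p_new of 0.2 to 0.3 and p_worse of 0.1 to 0.4:

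- c = 0, low end: 20 × 0.7 × 0.1 = 1.4 subjects.
- c = 0, high end: 20 × 0.8 × 0.4 = 6.4 subjects.
- c = 1: 0 subjects.

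Under these assumptions the answer runs from 0 to 6.4 of 20, and the documents do not fix c or either rate. The formula also pools all symptoms into any event, whereas Section 16 tests each adverse event separately, so even the upper figure is not the tested quantity.

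**The case against.** The best reply is that the plan has one definition of an adverse event, in Section 16, and that the other two texts only describe what staff say. That is correct. A reader might infer that worsening counts under one rule and not under another. The documents do not support this: the Section 4 answer is an aid to staff judgment, Section 8 describes an enquiry, and counting follows Section 16. The word updated is also undefined, so reading it as worsened is a natural inference but still an inference.

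The second reply is that worsening has other routes to notice. The side-effects rating after each session covers headache, fatigue, nervousness, dizziness and poor concentration, whether new or old. Staff must record any other concern about the subject at sessions and clinical assessments. MADRS and CAST cover mood, sleep, anxiety and irritability. This stands in part, because the trial would not be blind to deterioration. But the side-effects rating stops with the sessions, the staff item serves suicide-risk assessment, and no text links any of these to the adverse-event record.

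Third, a reader might infer that the narrower wording operates alone from day 14 onward. That is too strong. Ten sessions with none at weekends, within a three-week window, can run past day 14, so the Section 8 review may still be in use then. The narrower wording stands alone at the clinical assessments, not over a calendar period.

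Finally, this is a feasibility trial of 20 subjects whose primary outcome is session completion. That limits the consequence, but safety data are among the results that a pilot hands on to the next trial.

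**Conclusion.** The point holds as a gap in solicitation. The script asks for less than the Section 16 definition covers, and it is the only event wording for days 14, 30 and 60. Adverse events are therefore likely to be under-ascertained, and unevenly so across visits, where an existing symptom worsens without a new symptom or new treatment. This rests on the script being used as written, on subjects not volunteering what they are not asked, and on scale scores not being turned into adverse-event records. The size cannot be derived from the documents.

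A reader might go further and infer that the wording hides a difference between active and sham. That can be constructed: assume worsening in 50% of active and 20% of sham subjects, with new symptoms in 20% of each. The true any-event rates are then 1 − 0.8 × 0.5 = 60% and 1 − 0.8 × 0.8 = 36%, against 20% and 20% recorded if no worsening is captured by any route. But the split is assumed, and nothing in the documents supports it. Both blinded arms get the same question. If worsening is equally common, say 20% in each, both arms lose the same 36% − 20% = 16 points. Between-arm bias is possible but not shown.

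**What to change.** Use one event question in Sections 4 and 8, at every session and at days 14, 30 and 60. To the existing items on new symptoms and new medical conditions, add: *any worsening of symptoms or conditions you already had*. Keep the clause on newly started medication or treatment, because Section 4 relies on it to account for treatment changes in the analysis, and keep the reference to the last contact. Let Section 8 cite this question in place of its own phrase, which also removes the undefined word updated.

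Add one sentence to Section 16: worsening of a pre-existing symptom or condition reported in this review, judged against the last contact, is recorded as an adverse event and enters the per-event Fisher comparison. The reference point should be the same in both places; Table 1 shows no baseline administration of the side-effects questionnaire, so worsening from baseline would have no comparator there.

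The cost is one reworded question and one sentence. The downside is small: more events will be recorded in both arms, some of them fluctuations of the underlying illness.

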suicides per 100,000 person-years soon after hospital discharge among U.S. Army soldiers, almost 14-fold higher compared with the total U.S. Army. Previous suicidal behavior was one of the main predictors (OR=2.9) (34). Forte el al. (2019) addressed suicidal risk after hospital discharge in a review paper that included 48 studies with a total of 1,700,785 participants followed for almost 8 years after a psychiatric hospitalization (35). The authors noted that about 20% of the suicides and attempts had occurred within 15 days following hospital discharge and more than a quarter in the first month. The results also showed that mood disorders were associated with the highest risk (35).

These studies clearly show that evidence-based interventions for suicidal behavior prevention offered soon after psychiatric inpatient hospitalization are of major significance, especially for high-risk groups such as individuals with a history of SI and behavior and mood disorders. However, the low rate of outpatient treatment engagement and the high rate of dropout from an outpatient service after discharge from an emergency department is a challenge (36), and speaks to the need to overcome these barriers to care. Effective tDCS stimulation requires daily sessions, typically performed in an outpatient clinic. For some patients, this presents a serious barrier. Specifically, for patients in the first weeks after discharge, residual symptoms, and the need to reorganize personal issues and obligations after a period at the hospital may prevent them from commuting to daily visits at health facilities to complete a non-invasive brain stimulation treatment. Thus, to address low treatment engagement and overcome barriers to care with this population, this study will test the feasibility of a home-based tDCS protocol for preventing SI relapse soon after hospitalization discharge.

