5. INCLUSION AND EXCLUSION CRITERIA

Inclusion criteria:

- age between 18 and 65 years

- diagnosis of mood or bipolar disorder registered in the electronic hospital medical record

- history of suicidal ideation and/or suicide behavior at the time of admission registered in the electronic hospital medical record

- absent of suicidal ideation at the time of enrollment (defined as questions 1 and 2 of the C-SSRS answered "no").

- ability and willingness to provide information and permission to contact at least one person in the case of a need to contact them to promote subject safety or inability to reach the subject for follow-up

- a living situation with access to a private space suitable for administration of the RS-tDCS sessions in next three weeks

- agree to use a medically acceptable form of birth control while receiving the treatment if you are an individual able to become pregnant

- living in Monroe County region, as this is the area covered by the Mobile Crisis Team, a URMC psychiatric emergency team serving anyone within Monroe County

- device or computer with internet access for a URMC-approved remote RS-tDCS supervision

- ability to manage proper use of the device in a practice session

Exclusion criteria:

- acute psychiatric instability or substance abuse (e.g., psychotic symptoms, alcohol misuse in the previous three months, use of any illicit drugs in the previous three months)

- unstable medical condition with reduction of functional capacity

- history of epilepsy or seizures in the last year

- history of neurodegenerative diseases registered in the electronic hospital medical record
- presence of or implanted any ferromagnetic metal in the head or the neck
- pregnant or breastfeeding or willingness to become pregnant in the next month

- history of head trauma (e.g., head injury, brain injury) or neurosurgery
- history of skin disorder or sensitive skin area near stimulation locations
- the presence of pacemaker
- current treatment with electroconvulsive therapy or transcranial magnetic stimulation

Although concurrent treatment with medications or psychotherapy is not an exclusion criterion, we will measure changes in medication and psychotherapy for descriptive and planning purposes (please, see "Secondary outcome measures", item 9).

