9. RISKS TO SUBJECTS

Based on inclusion criteria of suicide crisis and the psychiatric inpatient recruitment setting, participants in this study are likely to have some increased risk for suicidal behavior (6, 33, 35). Thus, subjects must consent to remain in outpatient mental health care during the study. Consistent with URMC policy 5.4 (Patient Safety Plans Policy), a safety plan will be created for all inpatients enrolled in the study and reviewed by the subject's clinician prior to discharge. The plan includes a list of resources that the subject can call on when in need or at increased risk. If the subject declines to complete the safety plan, the clinician will make a note of this declination and provide crisis/safety resources. Finally, a copy of the safety plan is provided to the patient (subject), (and family/support person, as appropriate), and bookmarked in the patient's chart. There is a risk that the assessment and intervention may cause stress or discomfort. Subjects are informed of this during the consent process and given the option to decline to answer questions or discuss topics they do not wish to discuss. They can take breaks or stop a clinical assessment at any time. Research staff will promote subject comfort, including appropriate pacing of assessments and interventions, providing breaks, and discontinuing any clinical assessment when requested by a subject or it is clinically indicated.

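### The scripted treatment question prompts only for treatment started, so after the stimulation sessions end the record of co-treatment changes leans towards additions

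*Combined protocol and SAP*

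**What the plan says.** Section 5 (Inclusion and Exclusion Criteria) allows concurrent medication and psychotherapy and commits to recording how they change: "we will measure changes in medication and psychotherapy for descriptive and planning purposes". For the detail it refers to item 9 of the secondary outcomes, but that list in Section 4 ends at item 8.

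Item 8, the treatment emergent event review, is the only secondary outcome about treatment received outside the trial. On timing it says "after each RS-tDCS session and clinical assessment, subjects will be asked", and the question is given verbatim. It asks about new symptoms, "new medical conditions or been started on new medication/treatment since we last saw you". On use it says that "changes in treatment will help researchers to account for them in data analysis and the study's results interpretation".

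Section 8 (Study Procedures) adds a review of the subject's current treatment after each RS-tDCS session. For days 14, 30 and 60 it says only that the Table 1 questionnaires are used. In Table 1 the one row at those visits that touches treatment is the treatment emergent event review. Section 7 (Consent Process) lets staff take medication, among other things, from the hospital record.

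**The concern.** The commitment is to measure changes; the instrument asks about starts. A subject who has stopped a drug, had a dose altered or left psychotherapy can truthfully answer no.

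The direction matters because tDCS is tested as an adjunct to ongoing care. Section 2 says that "the high rate of dropout from an outpatient service after discharge from an emergency department is a challenge", and Section 9 states that "subjects must consent to remain in outpatient mental health care during the study". The plan thus recognises loss of care as a live possibility in this population, yet the question does not prompt for it. If the script is followed as written, the co-treatment record behind ideation, relapse, rumination, CAST and MADRS at days 30 and 60 will show additions more completely than withdrawals. That makes it a poorer basis for describing this pilot and planning the full trial.

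**Working it through.** The plan states no figure on this point, so the check compares the sources of treatment information and then works out the calendar.

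**Sources of treatment information**

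- *Item 8 question (Section 4)*: every session and days 14, 30 and 60. It prompts for new symptoms, new conditions and treatment started, but not for stops, dose changes or ended psychotherapy.
- *Review of current treatment (Section 8)*: described after each RS-tDCS session. It could reveal stops and dose changes, but is not described for days 14, 30 or 60.
- *Hospital record (Section 7)*: covers medication. No follow-up time points are given and psychotherapy is not listed.
- *Item 9 (cited in Section 5)*: does not exist, so the one pointer to a possibly fuller measure leads nowhere.

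During the session weeks, the Section 8 review can make good what item 8 omits. After the last session, item 8 is the only scheduled enquiry whose content is spelled out.

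**When the sessions end**

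Inputs: ten sessions, day 1 being the first, none at weekends (Section 8); a three-week window for sessions (Sections 1 and 4); last assessment at day 60 [+10], participation up to 70 days (Section 8).

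- Monday start: sessions on days 1–5 and 8–12, so the tenth is on day 12 at the earliest.
- Tuesday start: days 1–4, 7–11 and 14, so day 14. Wednesday, Thursday and Friday starts also give day 14.
- Window used in full: about day 21. Section 1 counts the three weeks from receipt of the device, so day 21 from the first session is an approximate upper end.

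**Length of the interval** (assessment day minus day of last session)

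| Last session | To day 60 | To day 70 |
|---|---|---|
| Day 12 | 60 − 12 = 48 | 70 − 12 = 58 |
| Day 14 | 60 − 14 = 46 | 70 − 14 = 56 |
| Day 21 | 60 − 21 = 39 | 70 − 21 = 49 |

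The range is 39–48 days to day 60 and 49–58 days to day 70. These figures are for subjects who complete all ten sessions; anyone who stops earlier has a longer interval. The day 30 and day 60 assessments always fall after the sessions. Day 14 may fall just after them, but the period leading up to it is largely covered by the session reviews.

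**Use in the analysis**

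Section 17 compares groups at each time point with a t-test or chi-square test and describes no adjustment for treatment changes. The realistic use of these data is therefore the descriptive and planning use named in Section 5.

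**The case against.** The strongest reply is that the treatment review in Section 8 is not a separate procedure. Table 1 has no row for it even at the sessions; the only matching row is the treatment emergent event review, which is also marked for days 14, 30 and 60. Section 8 may simply spell out how that row is carried out, in which case current treatment is reviewed at follow-up too. This reading is possible, and it rules out saying that nothing asks about stops after the sessions. It does not settle the matter: Section 8 ties the review to the sessions, no text extends it to the later assessments, and the only wording supplied still covers starts alone.

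The second reply is that subjects may volunteer a stop and the hospital record may show some medication changes. That stands, so the accurate statement is that stops are not explicitly prompted for, not that they are missed. Neither route is scheduled, and psychotherapy is not among the listed record items. Section 14 also allows a REDCap survey link when a subject cannot be reached by phone for follow-up; if item 8 is included there, the subject sees only its literal wording.

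The third reply is that the consequences are modest in a 20-subject feasibility pilot. That is correct. The primary outcome is session completion, which does not depend on this question.

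**Conclusion.** The point holds as a mismatch between what the plan undertakes to measure and what its script asks. For about 39–48 days up to day 60, or 49–58 up to day 70, stops, dose changes and ended psychotherapy are not explicitly prompted for. The descriptive co-treatment record is therefore one-sided towards additions. This rests on reading the Section 8 review as limited to sessions, which is where the text places it; the passages should be reconciled either way. The opening pages and the part between Sections 2 and 4 were not available and could not be checked.

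Three stronger conclusions that a reader might draw are not supported:

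- *That a given number of subjects will have unrecorded changes.* The documents give no rate of stopping or changing treatment. Any assumed overall rate would include additions, which the question does elicit, and changes in the session weeks, which the Section 8 review could catch.
- *That better recording would separate loss of background care from lack of tDCS effect.* With 20 subjects randomised 1:1 (about 10 per arm) and unadjusted comparisons, it would not. It would support description and planning.
- *That the plan names outpatient dropout as the main problem in this population.* Section 2 calls it a challenge, in arguing for home delivery, and does not rank it.

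The change is worth making because it is specific and nearly free, and because information not asked for during follow-up may not be recoverable later.

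**What to change.** 1. Reword the treatment part of item 8, for all sessions and for days 14, 30 and 60, to ask whether any medication, psychotherapy or other treatment has been started, stopped or changed in dose or frequency since the last contact.
2. State in Section 8 and Table 1 that the review of current treatment also applies at days 14, 30 and 60.
3. Correct the item 9 reference in Section 5 to the item that carries this measure. Item 8 appears to be the one, but the sponsor should confirm it.
4. Add to Section 17 a descriptive table of starts, stops and changes by arm at each time point.
5. Optionally, record at the same contacts a yes/no answer on whether the subject is still attending outpatient mental health care.

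The cost is slightly longer questioning at contacts already scheduled, plus the edits to the form and the protocol text. No visit is added, and neither the primary outcome nor any treatment rule is changed.
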